1.10. Study Subjects

The study involves adult human subjects.

NCORP practice sites will be randomized within a 2-arm cluster randomized design utilizing NCORP practice sites as the unit of randomization. A NCORP practice site will be defined as any practice location within an overarching NCORP designation where oncology physicians and study staff work independently (i.e., do not cross over into another practice site).

Study subjects will include:

- **Oncology physicians** at NCORP practice sites

- **Patients** will complete surveys and will also agree to have a clinical consultation with an oncology physician audio-recorded (baseline visit). Patients will have advanced cancer and various levels of functional status. Patients will be asked to identify a caregiver who may choose to participate in the study. As much as possible, caregivers should be recruited to be part of the study when the patient is recruited. In the rare circumstance that there is no willing caregiver to participate, the patient will be allowed to participate without a caregiver.

- **Caregivers** must enroll in the study before or on the baseline visit because they will accompany the patients during the clinic consultation that will be audio-recorded (baseline) and complete surveys.

2. STUDY OBJECTIVES

This is a cluster randomized study within the URCC NCORP network evaluating whether GA summary plus GA-driven recommendations can improve patient satisfaction with communication regarding age-related issues between patients, oncology physicians, and caregivers. The study has received support from the Patient Centered Outcomes Research Institute (PCORI) under their “Communication and Dissemination” portfolio. In addition, the National Cancer Institute (NCI) review was required which led to changes in the aims and statistical plan. The NCI review led to a new primary aim (satisfaction with communication regarding age-related issues) and the original PCORI primary aim (discussions about age-related issues during clinic consultation) became Secondary Aim 1.

2.1. Primary Aim (primary aim as specified by the NCI): To determine if providing geriatric assessment (GA) summary plus GA-driven recommendations to patients, their caregivers and oncology physicians **improves patient satisfaction with communication with the oncology physician** regarding age-related concerns.

Primary hypothesis: Patient satisfaction with communication with the oncology physician about age-related issues will be significantly higher in the intervention group compared to the control group.

The NCI primary outcome, patient satisfaction regarding communication about age-related issues as measured by a modified Health Care Climate Questionnaire (HCCQ-age), will be obtained via the Telephone Team Call, a phone call administered by trained personnel blinded to group assignment within 1 to 7 days of the baseline audio-recorded clinic consultation. The HCCQ-age will be mailed (with a return envelope) if a telephone call is not feasible. If the responses to the survey are not able to be obtained before the 4-6 week assessment, the HCCQ-age at 4-6 weeks will be utilized.

2.2. Secondary Aims

2.2.1. Secondary Aim 1 (primary aim as specified by PCORI): To determine if providing GA summary plus GA-driven recommendations to patients, their caregivers, and oncology physicians increases **discussions** about age-related issues during clinic consultation.

Hypothesis: A higher proportion of age-related issues will be discussed and addressed in the intervention group.

The outcome measure for this aim is the number of age-related discussions related to the different aspects of geriatric assessment that occur in the consultation clinic visit between the patient, oncology physician, and caregiver. The clinic visit will be audio-recorded. This outcome was accepted as the primary aim by PCORI.

2.2.2. Secondary Aim 2: To determine whether initially providing patients, their caregivers, and oncology physicians with GA summary plus GA-driven recommendations prior to their treatment influences **quality of life** of older patients receiving treatment and their caregivers.

2.2.3. Secondary Aim 3: To determine whether providing patients, their caregivers, and oncology physicians with GA summary plus GA-driven recommendations influences **caregiver satisfaction with communication** about age-related issues.

2.3. Exploratory Aims:

Exploratory aims will evaluate (1) whether the number of discussions about age-related issues during the clinic visit correlates with patient satisfaction, (2) whether the intervention increases the proportion of age-related concerns that are acknowledged and addressed, and (3) if communication about age-related issues influences how patients, caregivers, and oncology physicians make decisions for cancer treatment. An additional exploratory aim will examine the impact of the intervention on survival.

3. STUDY DESIGN

See Study Schema and Design for summary.

3.1. Choice of comparators

Because GA is not performed by community oncology physicians and this study ultimately will allow patients/caregivers/oncology physicians to choose their cancer treatments, a usual care comparator arm is appropriate and will allow for the accurate and appropriate assessment of how the intervention can improve communication about age-related issues and outcomes compared to current clinical practice. This study design is similar to previous studies that evaluated the impact of providing summarized HRQoL information to patients and oncology physicians on communication and outcomes. Usual care was the comparator arm in these cluster randomized studies.^{57,81}

3.2. Choice of study design

The study is designed as a cluster randomized trial because a care of service model is applied to each patient by the oncology team. If a cluster randomized design were not undertaken, there would be contamination in that oncology physicians could choose the care of service model if they were exposed to patients randomized to both arms. Given rapid changes that can occur in oncology practice with new supportive care and treatment agents, it is important to compare outcomes in the same time frame as would be possible in a cluster randomized study design compared to a “pre” versus “post” intervention study design.

4. PARTICIPANT ELIGIBILITY

4.1. Entry Criteria for Oncology Physicians

Oncology physicians must work at a NCORP practice site with no plans to leave that NCORP practice or retire at the time of enrollment into the study.

4.2. Entry Criteria for Patients

4.2.1. Inclusion Criteria for Patients

4.2.1a. Male or female 70 years of age or older

4.2.1b. Diagnosis of an advanced solid tumor malignancy (advanced cancer) or lymphoma. In most situations, this would be a stage IV cancer. A patient with a diagnosis of stage III cancer or lymphoma is eligible if cure is not possible or anticipated. Clinical staging without pathological confirmation of advanced disease is allowed.

Must be considering or currently receiving any kind of cancer treatment (any line), including but not limited to hormonal treatment, chemotherapy, monoclonal antibody therapy, or targeted therapy. Patients who are considering therapy are eligible even if they ultimately choose not to be on therapy. Patients with a history of any previous cancer treatment, including radiation and/or surgery are eligible. A patient may also be enrolled on a treatment trial and participate in this study, if all other inclusion and exclusion criteria are met.

4.2.1c. Have at least one geriatric assessment domain meet the cut-off score for impairment other than polypharmacy per Table 2.

4.2.1d. Have visits planned with the oncology physician for at least 3 months and be willing to come in for study visits.

4.2.1e. Able to provide informed consent or, if the oncology physician determines the patient to not have decision-making capacity, a patient-designated health care proxy (per institutional policies) must sign consent by the baseline visit.

4.2.1f. Subject has adequate understanding of the English language because not all GA measures have been validated in other languages.

4.2.2. Exclusion Criteria for Patients

4.2.2a. Have surgery *planned* within 3 months of consent. Patients who have previously received surgery are eligible.

4.2.2b. Have already made a decision to not undergo any cancer treatment (e.g., being followed in best supportive care or hospice).

4.3. Entry Criteria for Caregivers

A caregiver can be anyone, age 21 or over, who is able to understand spoken English and understand the study process and provide informed consent. One caregiver for each patient will be eligible and must be chosen by the patient. For the purposes of this study, a caregiver is defined as a valued and trusted person in a patient's life who is supportive in health care matters by providing valuable social support and/or direct assistive care. The caregiver accompanies the patient to medical appointments, is able to listen and give thoughtful advice and may be a family member, partner, friend, or professional caregiver.

4.3.1. Inclusion Criteria for Caregivers

4.3.1a. Selected by the patient when asked if there is a "*family member, partner, friend or caregiver [age 21 or older] with whom you discuss or who can be helpful in health-related matters;*" patients who cannot identify such a person ("caregiver") *can* be eligible for the study. A caregiver need not be someone who lives with the patient or provides direct hands-on care. A caregiver can be any person who provides support (in any way) to the patient.

4.3.1b. If a health care proxy signs consent for or with a patient, and wants to participate in the caregiver portion of the study, this same person will always be the caregiver selected. If a health care proxy does not want to enroll as a caregiver in the study or, if enrolled, chooses to stop their own participation in the caregiver portion of the study, but is able to assist the patient in completing the study, the patient can still participate. In other words, the health care proxy can choose NOT to participate in the caregiver portion of the study. This does not preclude the patient from participating in the patient portion of the study with the health care proxy's assistance.

4.3.2. Exclusion Criteria for Caregivers

4.3.2a. Caregivers unable to understand the consent form due to cognitive, health, or sensory impairment will be excluded.

5. IDENTIFICATION, RECRUITMENT, AND CONSENT PROCEDURES

Patients and their caregivers will be recruited from the outpatient community oncology practices affiliated with the URCC NCORP Research Base network. The results of this study will be generalizable to the majority of older adults with cancer and their caregivers because it will include older cancer patients and their caregivers from diverse backgrounds and at varying health statuses.

5.1. Study Participants (Patients and Caregivers)

Study participants will be identified by their treating oncology physicians, who enroll in the study, the nurses that work with the enrolled oncology physicians, and the clinical research associates (CRAs). The CRAs will work closely with the enrolled oncology physicians and nurses to identify patients aged 70 and over with advanced cancer. The oncology physician then confirms if the patient is an eligible study candidate for all requirements other than GA impairment by completing the eligibility checklist with the CRA and signing it. The oncology physician or CRA will introduce the study to the eligible patients and/or their designated health care proxies/caregivers, and will provide them with an IRB approved study brochure and consent to review. Adequate time will be provided to the patient and/or the designated health care proxy to read the consent. By this time, the patient should have selected a possible caregiver. The CRA, the oncology physician, and the nurses are available to answer any questions the patient and/or caregiver/healthcare proxy may have about any aspect of the study prior to consenting and throughout the entire study period. Patients and/or their designated health care proxies and caregivers may choose to sign the appropriate (patient or caregiver) informed consent documents immediately on the day the study information is presented to them or they may choose to take the consent forms home and discuss them with others; then if they decide to participate in the study, they can provide signed consent forms the next time they meet with the CRA or oncology physician.

5.1.1. Informed consent will be obtained from the patient, unless they lack capacity to provide consent. If a patient lacks capacity, a health care proxy will be required to sign consent per institutional or local policies on consent for incapacitated/decisionally impaired subjects. If the patient does not have an appointed health care proxy on or before the baseline visit, he/she will not be enrolled onto the study. All consent documents will be signed by the patient and/or designated health care proxy and maintained in the patient record with copies provided to the patient and/or designated health care proxy.

5.1.2. The screening measures will then be performed. Those with a diagnosis of dementia, as noted in their medical record or diagnosed by a physician, or who meet the cut-off score for impairment on the cognitive screen (score of 11 or more on Blessed Orientation-Memory-Concentration Scale) can be included if a designated health care proxy selected by the subject signs the consent. The goal of the intervention is to improve outcomes of older cancer patients with all underlying health conditions including cognitive issues. Therefore we will include these patients and will conduct the assessments with assistance of the proxy. The health care proxy should agree to participate in the study as the caregiver. If a health care proxy chooses to stop their own participation in the study, but is able to assist the patient in completing the study, the patient can still participate.

5.1.3. Ethical standards for human subjects will be strictly followed in accordance with local policies and/or institutional review board requirements on the enrollment of adult decisionally incapacitated research subjects and permission of authorized representatives.

5.1.4. Current, state, federal, and institutional regulations concerning informed consent will be followed. Participation in this study is voluntary. Participants are free not to take part or to withdraw at any time, for whatever reason, without risking loss of present or future care they would otherwise expect to receive. In the event that a patient does withdraw from the study, the information they have already provided will be kept in a confidential manner. Data will be used unless permission is revoked in writing and sent to their oncology physician or the URCC study team. Site oncology physicians will be directed to forward any such correspondence to the URCC Research Base.

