5.2. Oncology Physician Recruitment

Because oncology physicians are being recruited and enrolled from sites across the country by the URCC Research Base, oncology physicians will read and agree to participate either via Research Electronic Data Capture (REDCap) or on paper if REDCap is not a feasible option. REDCap is a software toolset (see Section 16.3 for more information) for electronic collection and management of research and clinical trial data developed by Vanderbilt University. Oncology physicians will be enrolled prior to enrolling (screening registration) their first eligible patient. Staff from the URCC Research Base (including the PI) will be available to answer any questions the oncology physicians may have over the phone. Procedures for the oncology physicians are minimal risk and involve: completing surveys that will be de-identified, and identifying patients for the study.

Oncology physicians will provide baseline demographic information, fill out a baseline survey that evaluates preferences for decision-making, and help identify their own patients who may be eligible for the study. The baseline survey can be completed online via REDCap or on paper if REDCap is not feasible. REDCap will securely store the oncology physician's email address for surveys. In addition to the email address, the only personal identifying information the oncology physicians will provide will be their name, age, ethnicity, and the name of the clinic where they work. The oncology physician will be assigned an ID number, which will be used to link their surveys together with those of patients enrolled in the study.

The oncology physician also will agree to have one visit per each patient audio-recorded (baseline). All parties present for recorded office visits, including: enrolled patients, any accompanying caregivers, family or friends, the oncology physician, and any other physicians or health care providers not participating in the study will be fully aware that the conversation is being audio-recorded and will provide verbal assent immediately before any recording begins, in addition to the prior written consent of enrolled subjects. These audio-recordings will be labeled and stored using the patient's initials and date.

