9. NCORP PRACTICE SITE RANDOMIZATION

A practice site is defined as any practice location within an overarching NCORP designation where oncology physicians and study staff work independently, i.e., do not cross over into another site. Practice sites will be randomized to one of the two study arms by means of a computer-generated randomization table. The randomization process will be determined using R software provided by [name], the lead biostatistician of the URCC NCORP Research Base.

Sites are randomized on a continual basis due to a variety of factors (i.e., a new NCORP Community Affiliate has been added to the URCC NCORP Research Base network, a new oncology practice site has been added to an existing NCORP Community Affiliate, or an oncology practice site that is currently affiliated with an NCORP Community Affiliate has expressed interest in participating in the COACH study). Past accrual to URCC studies (or NCORP Cancer Control studies if URCC accrual information is not available for new Affiliates and sites) is used to stratify each practice site as a **large** accruing (20 or more accruals/year) site or a **small** accruing (less than 20 accruals/year) practice site in order to assure balance in the randomization. The general assumption will be that any new site will be considered "small", unless it is determined based on past accruals that they are large. For new oncology practice sites that meet the definition for being independent (i.e., physicians and staff that do not cross over into another site), the next unassigned randomization allocation, from the randomization table will be used to assign their study arm. The randomization table takes into account size of the practice site. If a new oncology practice site is added at a later time during the study with physicians/staff that also see patients (cross over) at both or multiple practice sites, the new practice site will be assigned to the same study arm as the already randomized practice site where the physician/staff also sees patients.

Once sites have IRB approval on file with the Research Base and at least one member of research staff is trained on all study procedures, they are notified of their randomization allocation by an email from the study PI, [name]. Practice sites names and randomization assignments are saved in the database, this is used to link to which arm each study patient belongs to during patient registration.

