10. INTERVENTION OVERVIEW FOR PHYSICIANS

Practice sites will be notified if they are in the intervention arm by URCC Research Base staff. Prior to the intervention, oncology physicians will receive training on how to best utilize GA information in clinical practice for older adults with cancer. The training session provides a brief overview of the intervention information and can be completed through a web conference, telephone call, or as a paper “sign-off” documenting review of the materials. The training materials were developed with resources from Drs. [name]’s and [name]’s geriatric oncology lectures.

The CRAs and/or research nurses at sites randomized to the intervention arm will be trained to utilize the [mycarg.org website](http://mycarg.org) to derive a summary of GA scores and a list of targeted GA-driven recommendations.

This information will be printed by the site CRAs for the oncology physician who will “sign off” that he/she has received and reviewed the information. Study or clinical staff can assist the physician in checking which recommendations were considered and facilitating implementation of GA-driven recommendations. Two copies of the summary and checklists should be made: one should be provided to the patient/caregiver and one should be retained in the study chart. Patients and caregivers should be provided with a copy of the GA summary and GA-driven recommendation forms prior to the audio-recorded visit. The original forms should be submitted to the URCC Research Base.

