11.1.2. Subject Identification Process

11.1.2a. Patients: Once a site is IRB approved, the site study staff can start screening for patients according to the inclusion/exclusion criteria for patients (Section 4.2). Only patients from enrolled physicians can be registered.

11.1.2b. Screening Log: A screening log will be kept at each participating site, where *both* patients and caregivers approached for the study will be entered by site study staff.

11.2. Screening: VISIT 0

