11.3.1. Patient & Caregiver Assessment Process

11.3.1a. BEFORE BASELINE VISIT:

Site study staff will telephone the participant to:

- Confirm scheduled visit with the oncology physician.
- Confirm that the patient and caregiver completed the screening surveys before the oncology physician visit and remind them to bring the surveys in with them.
 - Schedule the patient to come in to meet with site study staff at least 45 minutes prior to the oncology physician visit in order to complete study procedures. Allow for more time if patient and caregiver communicate(s) that surveys have not been completed. Only patients who complete GA procedures can be registered for the study.

11.3.1b. AT THE BASELINE VISIT:

- If the patient’s screening surveys have not been completed prior to the patient coming in, complete them now.
- If the caregiver’s surveys have not been completed prior to the caregiver coming in, complete them now.
- If not complete staff should administer cognitive, physical performance, and nutrition assessment.
- If not complete, staff should complete CRA study forms.

- If not complete, complete baseline surveys. The baseline surveys do not need to be completed prior to registration, but should be completed on the day of the baseline visit. For example, patients can complete baseline surveys while receiving cancer treatment that same day.
- Score each GA measure as taught in the training procedures. If assistance is needed for scoring, contact the URCC NCORP Research Base.
- Patients who have at least one abnormal GA score other than polypharmacy can move forward with the study.
- After the GA and the above steps are complete, the baseline registration procedures can be completed for the patient and caregiver (refer to section 6, Registration).
 - Registration must occur prior to baseline study visit with the oncology physician.
- Prior to the study visit with the oncology physician, if depression (GDS) or cognition (BOMC) assessments score ≥ 11 , inform patient's oncology physician as follows:
 - Usual Care arm -- inform oncology physician with template as per training.
 - Intervention arm -- information on cognitive impairment or depression is included in summary (see section 11.3, *Intervention Procedures*).

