## **3 Study Methods**

### **3.1 General Study Design and Comparators**

[figure not shown]
The study design is a cluster randomized clinical trial. The intervention is designed to try to improve communication about age related concerns between oncology physicians, patients and their caregivers. Study subjects include oncologists, patients and their caregivers. Sites within the URCC

NCORP network are randomized prior to the enrollment of any subjects at any site. Sites in both arms (control and intervention) will conduct the GA on all subjects. Physicians at sites randomized to the intervention arm will be provided with a GA summary and GA-driven recommendations. Since the GA is not part of community oncology physicians’ standard of care, a usual care comparator arm is appropriate and will allow for the accurate and appropriate assessment of how the intervention can improve communication about age-related issues and outcomes compared to current clinical practice. This study design is similar to previous studies that evaluated the impact of providing summarized HRQoL information to patients and oncology physicians on communication and outcomes. Usual care was the comparator arm in these cluster randomized studies.

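### Site staff who know the arm choose which patients to approach, yet baseline geriatric impairment enters the models for the primary aim and Secondary Aim 1 only if an imbalance is seen

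*Protocol*

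**What the plan says.** **Order of events.** SAP 3.1 says that sites within the URCC NCORP "network are randomized prior to the enrollment of any subjects at any site". Under Protocol 9, once IRB approval is on file and at least one staff member is trained, "they are notified of their randomization allocation by an email from the study PI". Protocol 10 adds: "Practice sites will be notified if they are in the intervention arm by URCC Research Base staff". Intervention physicians are also trained in using geriatric assessment (GA) information.

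**Who is approached.** Protocol 5.1: "Study participants will be identified by their treating oncology physicians, who enroll in the study, the nurses that work with the enrolled oncology physicians". Clinical research associates do so as well. Protocol 5.2 asks physicians to "help identify their own patients who may be eligible for the study". Neither these sections nor Protocol 11.1.2 and 11.2.1 require consecutive or list-based approach, or a recruiter unaware of the arm.

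**Entry criterion.** Protocol 5.1: "The oncology physician then confirms if the patient is an eligible study candidate for all requirements other than GA impairment". After consent, site staff administer and score the GA, and Protocol 11.3.1b says "Patients who have at least one abnormal GA score other than polypharmacy can move forward with the study".

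**Records.** Protocol 11.1.2b: "A screening log will be kept at each participating site". It covers patients and caregivers who were approached.

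**Models.** Protocol 15.1 and SAP 4.1 name study site, oncologist type, gender, age, race/ethnicity, cancer type and treatment status. They then say that a key covariate will be added if the arms turn out to differ on it. Protocol 15.2 and 15.3 and SAP 4.2 and 4.3 apply this framework to the primary aim and Secondary Aim 1. GA impairment is a planned model term only for Secondary Aim 2 (Protocol 15.4.1, SAP 4.4.1).

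**The concern.** Randomising sites balances sites. It does not balance patients who are chosen after the site knows its arm. A physician who will receive a GA summary may be more inclined to put forward patients with evident geriatric needs, or patients with whom the relationship is good. A usual-care physician may choose differently.

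Impairment plausibly affects how many age-related matters come up at the visit (Secondary Aim 1) and how satisfied the patient is with the discussion (primary aim). Rapport matters too, because HCCQ-age rates the treating physician, and Protocol 11.2.1a expects only some patients to be new to that physician. The first HCCQ-age is collected after the recorded visit, so there is no earlier value to reveal or adjust for a difference. A difference created at recruitment would add to the estimated intervention effect or mask it, and more sites or patients would not remove it.

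**Working it through.** **1. Reproduce the plan's figure.** Inputs from Protocol 15.2: SD 2.1; ICC 0.14 (95% CI 0.01 to 0.51); k = 8 sites per arm; m = 31 per site; 80% power; level 0.05, taken as two-sided.

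SE = SD × √(2 × (1 + (m − 1) × ICC) / (k × m))

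At ICC 0.14: 2.1 × √(2 × 5.2 / 248) = 0.430. The detectable difference from the noncentral t with 2k − 2 = 14 df is 1.30 points, and the plan states 1.3. At ICC 0.01 and 0.51 it is 0.65 and 2.29, against the stated 0.6 and 2.3. Accrual: 31 / 0.95 rounds up to 33 per site, and 16 × 33 = 528, as stated.

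**2. Add a selection shift and no true effect.** The documents give no figure for such a shift, so 0.1, 0.2 and 0.3 SD (0.21, 0.42 and 0.63 points) are assumptions. A shift of 0.42 would arise, for example, if 20% of one arm's patients scored 1 SD higher through selection: 0.20 × 2.1 = 0.42.

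The rejection rate comes from the noncentral t with noncentrality shift / SE. For 0.42 points with 16 sites this is 0.42 / 0.430 = 0.98.

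**3. Repeat with the 68 sites reported in Protocol 15.2.** Assume equal, independent sites and the same 16 × 31 = 496 evaluable patients: k = 34, m = 496 / 68 = 7.29, 66 df. At ICC 0.14 the SE is 0.259, and the noncentrality for 0.42 points is 1.62.

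Chance of a significant result with no true effect (nominal 5%):

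| Assumed shift | 16 sites, ICC 0.14 | 16 sites, ICC 0.51 to 0.01 | 68 sites, ICC 0.14 | 68 sites, ICC 0.51 to 0.01 |
|---|---|---|---|---|
| 0.21 | 7.4% | 5.8% to 14.9% | 12.6% | 8.3% to 18.6% |
| 0.42 | 14.9% | 8.1% to 44.4% | 36.0% | 18.8% to 56.7% |
| 0.63 | 27.7% | 12.1% to 77.8% | 67.0% | 36.1% to 89.1% |

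More sites shrink the SE, so a fixed bias is declared significant more often.

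**4. Independence of the 68 sites.** The sample table in SAP Appendix A shows many rows sharing one Rand ID. If those sites were allocated together, there are fewer independent units, and the true rates lie nearer the 16-site columns.

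**The case against.** **GA scoring as a way to steer entry.** A reader might infer that staff who know the arm could do this. It is at most a minor route. The physician confirms every criterion except GA impairment. The GA follows consent, so scores are not known at approach. Apart from the cognitive and physical performance tests the tools are self-administered, all have fixed cut-offs (Protocol 8.1), and scores are confirmed at registration (Protocol 6.2.3).

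**Impairment shut out of the model.** A reader might infer this too. It is not so. The covariates are given as examples, and the imbalance clause could bring impairment in. What stands is that the clause has no list or threshold and is applied after the data have been seen.

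**No baseline information on the relationship.** PEPPI, the patient's confidence in dealing with physicians, is scheduled at baseline, and Protocol Appendix X-1 (1.4.2) reports correlations of 0.49 and 0.51 with satisfaction with the physician's manner and communication. It is a partial proxy: it is not a planned covariate, and baseline surveys may be completed later on the visit day.

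**Patients passed over will go unreported.** Appendix C of the SAP starts at screen registration, after consent, but the Appendix D diagram is not shown and may include approach counts.

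**Other points that stand.** The shifts are assumed. Need and rapport might pull satisfaction in opposite directions. Screening may open at IRB approval, slightly before notification, so a few candidates could be identified earlier. Blinded callers protect collection of the outcome, but not who enters. Requiring approach in list order would come late: SAP 3.4.1 gives 479 evaluable or 413 enrolled of 528, leaving 49 or 115. The physician's discretion over eligibility would also remain.

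**Conclusion.** The concern holds as a risk that the analysis plan should anticipate. Recruitment by people who know the arm is documented, and baseline impairment, one characteristic on which selection could act, is left to a data-driven rule in the two analyses where it matters most.

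The documents do not support the stronger conclusion that selection bias occurred, or any statement of its size or direction. The 15% and 36% for a 0.2 SD shift are illustrations. They rest on the assumed shift, the planning SD, ICC 0.14 and, for 36%, on 68 equal and independent sites. The 67% for a 0.3 SD shift needs all of these conditions and should not be read as an estimate for this trial. Cluster randomisation itself is not in question.

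**What to change.** **Analysis.** In SAP 4.1 to 4.3 and Protocol 15.1 to 15.3, prespecify the baseline number of impaired GA domains (Protocol 8.1, Table 2) as a fixed covariate for the primary aim and Secondary Aim 1, regardless of observed imbalance. State whether polypharmacy counts, since it does not count for entry. The GA precedes baseline registration, and Protocol 11.3.1a requires it for registration, so the covariate is available for all patients and cannot be altered by the intervention.

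**Reporting.** Report by arm the numbers approached, consented, GA-ineligible and enrolled, from the existing screening log and registration records, together with baseline GA impairment. Numbers eligible but never approached cannot be recovered from that log and should not be promised.

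**Limitation.** State that the covariate does not remove selection on rapport or on anything else unmeasured.

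**Cost.** A wording change, one model term and one table, all from data already collected and applicable to patients already enrolled. No change to recruitment is proposed.
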